customized list of patients for each physician. The treating physician indicates whether IU-PBRN should approach a patient for enrollment in the study. Eligible patients will be approached by research assistants (RAs) at their next scheduled appointment. The patient's preference and any initial screening information are recorded at this session using portable computers. Electronic data management ensures that patients' and physicians' preferences are stored, retrieved, and delivered to minimize inconvenience to both parties and to maximize the efficiency of the RAs. We will use the IU-PBRN experience and research recruitment infrastructure to identify older adults for RAs to approach for potential participation into our pragmatic dementia screening trial.

Not all inclusion and exclusion criteria can be reliably assessed through the INPC data available to the IU-PBRN. A final determination of the subject's eligibility is made during the face-to-face encounter in clinic with the IU-PBRN RA. We will exclude any subject who:

- are a permanent resident of a nursing facility;
- have a serious mental illness such as bipolar disorder or schizophrenia as determined by the presence of related ICD-9 codes indicative of such an illness; or
- have a pre-existing diagnosis of dementia or cognitive impairment

The list of inclusion and exclusion criteria will be given to the PBRN coordinator to arrange for subject contact during their next primary care visit. Based on our previous dementia related studies in the targeted primary care systems^{22,33,34,100,107}, we anticipate approaching 6,000 older adults to enroll 4,000. Rolling enrollment will take place over 30 months with an approximate monthly enrollment rate of 130 subjects. As outlined in the figure above, we anticipate that the dementia collaborative care program will manage 100 subjects with dementia. They will also counsel 100 subjects regarding the future impact and management of their diagnosis of mild cognitive impairment and assure them that their cognition is normal

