despite their positive screening results. The entire 4,000 subjects will be followed for 12 months. Across the various primary care practices, we will have access to more than 12,000 adults aged 65 and older. From our prior screening studies, we know that the prevalence of screening positive for possible dementia is 13-15% and of these, 50% will have dementia on subsequent diagnostic assessments. Although we have designed this study as a pragmatic trial, we will be requesting that patients sign informed consent for participation in the project.

Telephone Recruitment:

We will also employ a telephone version of the informed consent process to allow for potential recruitment of previously identified eligible patients via the INPC that were not approached in clinic by the ResNet team due to time and prioritization restraints. We will obtain a list of the eligible participants that were not approached from the PBRN Program Manager on a regular basis. These participants will be contacted for participation by telephone by study research assistants. We will also utilize the same telephone consenting process to recruit subjects attending the IU Health Arnett primary care clinics. Eligible patients from the IU Health Arnett primary care clinics will be identified by the treating physician and a list generated for the study research team.

Screening Process

Both subjects who are randomized into the non-screening arm of the study and those who are randomized into the screening arm will complete a set of standardized questions about successful aging, preventive health measures, and lifestyle behaviors. This is to invest the patients randomized into the non-screening arm of the study in the project, minimize the potential excess focus on cognitive screening alone, and to remove any impressions among the “non-screened” group that they missed out on an important health screen. We have not pre-specified the content of this screener because it will be designed based on ongoing data collection in the two targeted health care systems. This is consistent with our approach to embed the project, whenever possible, into ongoing or emergent activities. Examples of

questions to include in this control questionnaire might include: smoking, physical activity, influenza vaccination, or seat belt use for example. At the time of this questionnaire, enrolled subjects will also complete the baseline study assessment described later in this proposal.

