Through the systematic review described in the Preliminary Studies section, we have identified a screening instrument that meets the following criteria: 1) demonstrated validity in primary care settings; 2) requires less than five minutes to administer; and 3) has a positive likelihood ratio (LR) of 5 or higher. Based on our systematic evidence review for the literature that was published in *JAMA* in 2007⁷⁸, we selected the Memory Impairment Screen Telephone version (MIS-T)⁹⁶ as the screening instrument. The MIS-T takes only four minutes to complete with excellent inter-rater reliability, has been validated in multiple primary care and community samples, and has a positive LR of 33.^{6,96-99} The MIS-T has a total score from 0 point to 8 points. A cut-score < 5 has 86% sensitivity and 91% specificity for dementia with a positive predictive value of 72% and negative predictive value of 96% in a setting with a dementia prevalence of 15%.^{6,96-99} The MIS-T will be administered by the study research assistants after the subject consents to be enrolled in the study and randomized into the screening arm of the study.

Subjects who are randomized into the screening arm of the trial and score less than 5 points on the MIS-T will be referred to the collaborative dementia care program for a subsequent diagnostic assessment, counseling and management. We are not expecting the primary care practice to complete this next step. Among the 300 patients who will score less than 5 on the MIS-T (15% positive screening rate), we anticipate that approximately 100 (a refusal rate of 33%) will refuse follow-up diagnostic assessment, 100 subjects will not be diagnosed with dementia despite their positive screening results, and 100 subjects will be diagnosed with dementia.

Why not simply rely on the primary care practice to deliver the Collaborative Care Program?

Given that this is a pragmatic trial, reviewers might question whether the provision of the collaborative care program moves this project too close to an explanatory design. Our research team did

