Statistical Power, derived from sample size estimate, is used to test the primary hypothesis that subjects in the screening group will have higher health related quality of life than the no screening group. Previous randomized trials comparing collaborative care to usual care in demented patients have stated effect size of 0.4 being clinically significant.^{34,35} Considering that the majority of patients in the screening group or the no screening group are not demented, the observable effect size between these two groups will be a combined effect size measure in the non-demented subjects and in those demented subjects receiving the collaborative dementia care program.

Assuming 85% sensitivity of screening instrument and 15% prevalence of dementia in this patient population, to achieve 80% power to detect a significance effect size of 0.094 between the screening group and the no screening group at $\alpha=0.05$ level (two-sided), and allowing 10% of patients with missing follow-up outcomes at 12 months, we need to enroll at least 3951 patients into the study. The effect size of 0.094 between the screening group and the no screening group reflects a difference of 0.40 SD between demented patients in the collaborative dementia care program and demented patients who were not screened and a difference of 0.06 SD in the majority of patients who are not demented in either group. We demonstrate in the table below that our planned sample size of 4,000 will have sufficient power to detect significant differences between the “screen” group and the “no screen” group under various scenarios assuming varying degrees of efficacy measures for the collaborative dementia care program and for the screening only subjects.

Estimated power with a total sample size of 4,000 comparing primary outcome measures between the screening group and the no screening group (two-sided at $\alpha=0.05$) allowing 10% of patients with missing outcomes at 12 months.			
Effect size of collaborative care in demented subjects	Effect size In non-demented subjects	Observable Effect Size	Power Estimate
0.3	0.07	0.091	77.9
	0.08	0.100	85.1
0.4	0.07	0.102	86.4
	0.08	0.110	91.0

For the Secondary Aims, given the sample size of 4000, we will have greater than 95% power to test the equivalence levels in PHQ-9 and GAD-7 at 1 month assuming equivalence differences of 0.6 (SD=5.1) on PHQ-9 and 0.5 (SD=3.2) on GAD-7 based on our previous studies in primary care patients.^{34,51,93,114-118}

J. Limitations

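### The primary power calculation assumes 15% dementia prevalence, but the protocol expects about 6% demented and 5% managed; unadjusted power is then about 61–64%, not 80%

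*Combined protocol and SAP*

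**What the plan says.** Section I, Statistical Power, sets the dementia share for the primary hypothesis: "Assuming 85% sensitivity of screening instrument and 15% prevalence of dementia in this patient population, to achieve 80% power". The target effect is 0.094 SD. It is described as a blend of 0.40 SD in demented patients receiving collaborative care and "a difference of 0.06 SD in the majority of patients who are not demented in either group". With two-sided alpha 0.05 and 10% missing at 12 months, the paragraph asks for at least 3951 patients. A table for 4,000 patients varies the two component effects (0.3 or 0.4; 0.07 or 0.08) and gives powers of 77.9, 85.1, 86.4 and 91.0%.

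Other sections describe the same population differently:

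- Section E, Subject Recruitment: "we anticipate that the dementia collaborative care program will manage 100 subjects with dementia", and "the prevalence of screening positive for possible dementia is 13-15% and of these, 50% will have dementia".
- Section E, Screening Process: "Among the 300 patients who will score less than 5 on the MIS-T (15% positive screening rate"; of these, "100 (a refusal rate of 33%) will refuse follow-up diagnostic assessment, 100 subjects will not be diagnosed with dementia", and the remaining 100 are diagnosed with dementia.
- Section L puts dementia at about 6% of the target population under risks to subjects, and at no more than 6% of the sample under the consent procedure.

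The only other 15% dementia prevalence is in Screening Process, where the MIS-T predictive values are quoted "in a setting with a dementia prevalence of 15" per cent. That describes the instrument's reference setting, not this trial's enrollees.

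**The concern.** The overall effect is mostly small effects in non-demented patients plus a large effect in the few who reach the care program, so it depends strongly on the treated share. Sensitivity of 85% applied to 15% prevalence implies 12.75% treated, or 255 of 2,000. The operational sections plan for 100. The table varies the component effects but never the prevalence or the uptake, so it does not test the input in doubt.

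If power is really in the low 60s, the type II error is 36–39% rather than 20%. A null HUI result could then be read as evidence that screening brings no benefit, in a trial meant to inform policy.

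**Working it through.** **1. Reproduce the plan.** Two-sample t-test (noncentral t), two-sided alpha 0.05, effect 0.094 SD: 80% power needs 1,778 per arm, and 2 × 1,778 / 0.9 = 3,951, as stated. With 4,000 enrolled and 10% missing there are 1,800 per arm. The powers at 0.091, 0.100, 0.102 and 0.110 SD are then 77.9, 85.1, 86.4 and 91.0%, as tabulated. At 0.094 the power is 80.5%, and the smallest effect with 80% power is 0.0934 SD. So the calculation is unadjusted and correct once the effect size is given.

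**2. From components to 0.094.** The stated inputs give 0.15 × 0.85 = 0.1275 treated.

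- Rule B (missed cases and refusers get no effect): 0.1275 × 0.40 + 0.85 × 0.06 = 0.102.
- Rule A (everyone outside the program gets 0.06): 0.1275 × 0.40 + 0.8725 × 0.06 = 0.103.

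Neither is 0.094, so the mixing rule is not the one the text suggests. With a non-demented weight of 0.85 and rule B, all five stated effects are met, at the edge of rounding, by a treated share of 0.10625. Other nearby pairs of weights also fit, at about 0.108 treated with 0.84 non-demented. Rule A gives no common solution. Either way the implied treated share is near 10.6–10.8%, about twice the planned 5%.

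**3. Check 15% against the planned patient flow.** Section E states: "A cut-score < 5 has 86% sensitivity and 91% specificity for dementia". The expected positive rate is 0.86 × prevalence + 0.09 × (1 − prevalence).

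| Prevalence | Screen-positive |
|---|---|
| 15% | 20.55% (411 of 2,000) |
| 8.8% | 15.8% |
| 6% | 13.6% |

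The plan expects 13–15% positive. The 8.8% is the prevalence implied by a detected yield of 7.5% (half of 15%) at 85% sensitivity: 0.075 / 0.85 = 0.088.

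**4. Power at the protocol's own shares** (0.40 and 0.06 SD, 1,800 per arm):

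| Input set | Treated | Non-demented | Effect (SD) | Power |
|---|---|---|---|---|
| 15% positive, half demented, one third refuse | 0.05 | 0.912 | 0.0747 | 61.1% |
| 100 managed, 6% demented | 0.05 | 0.94 | 0.0764 | 63.0% |
| 100 managed, rule A | 0.05 | 0.95 (all others) | 0.0770 | 63.7% |
| 6% × 85% × 67% uptake | 0.034 | 0.94 | 0.0701 | 55.6% |
| 7.5% yield, no refusal | 0.075 | 0.912 | 0.0847 | 71.9% |
| 7.5% yield, no refusal, rule A | 0.075 | 0.925 (all others) | 0.0855 | 72.7% |

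Rule B applies unless rule A is stated. Example, first row: 0.05 × 0.40 + 0.912 × 0.06 = 0.020 + 0.0547 = 0.0747.

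**5. The power table at 5% treated:**

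| Demented / non-demented effect | Stated | At 5% treated |
|---|---|---|
| 0.3 / 0.07 | 77.9 | 66–69 |
| 0.3 / 0.08 | 85.1 | 75–78 |
| 0.4 / 0.07 | 86.4 | 71–74 |
| 0.4 / 0.08 | 91.0 | 80–82 |

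The table has no row for the 0.06 base case. Such rows would read about 55–58 (with 0.3) and 61–64 (with 0.4).

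**6. What ANCOVA could add.** Taking the effects in unadjusted SD units, adjustment for a baseline with correlation ρ raises the effective size to d / √(1 − ρ²). At 5% treated (0.0747–0.0764 SD), power is 73.5–75.4% at ρ = 0.5, 80.0–81.7% at 0.6 and 88.0–89.4% at 0.7. These values of ρ are assumptions. The ρ needed for 80% is √(1 − (d / 0.0934)²): 0.60 at 0.0747, 0.575 at 0.0764 and 0.57 at 0.0770. Over the range in step 4 it runs from 0.40 to 0.66.

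**The case against.** The best defence is that the primary test is a baseline-adjusted ANCOVA, for which the power paragraph takes no credit. A correlation of 0.6 would bring power back to about 80%, and 0.7 would exceed it. That stands as a possibility, so it is not shown that the trial is underpowered. But the documents give no baseline-to-12-month HUI correlation. The ICC of 0.75 in Section H is test-retest reliability in mild dementia, which is a different quantity in a different population.

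Second, 56–73% holds the effects at 0.40 and 0.06 SD, and its ends combine figures from different sections. This is correct. The 3.4% end implies about 68 managed rather than the stated 100, and the 7.5% end ignores the stated refusals. The range is for the base case tied to 80%; with 0.4 and 0.08 SD, power at 5% treated is 80–82%.

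Third, the central figure depends on the effect given to missed cases and refusers. It does, but only by about one to three points (64% instead of 61–63%).

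Fourth, the screen-positive check is imperfect. At 15% prevalence, the stated sensitivity and specificity give a positive predictive value of 63%, not the quoted 72%; at 6% they give 38%, not the planned half. That check is supporting evidence only. The conflict rests on the protocol's direct statements.

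**Conclusion.** The concern holds. The 15% prevalence behind the primary power calculation conflicts with the protocol's own expectation of about 6% demented and 5% managed, and no text reconciles them. On the plan's unadjusted basis, with 0.40 and 0.06 SD and 1,800 per arm, power is 61–63% at 5% treated, or 64% if missed cases and refusers also get 0.06 SD. It is 56–73% over the other input sets, none of which reaches 80%. In addition, the stated inputs give 0.102–0.103 SD rather than 0.094, so the derivation cannot be followed as written. Whether the planned ANCOVA reaches 80% depends on a correlation that the documents do not supply. The statement must be corrected because it is the sample-size justification for the primary hypothesis.

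**What to change.** In the Statistical Power paragraph:

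1. Choose one input set and reconcile it with Sections E and L. The candidates are not equivalent. Section E (15% positive, half demented, one third refusing) gives 5% treated, 0.075 SD and 61%. Section L's 6%, with 85% sensitivity and 67% uptake, gives 3.4% treated, 0.070 SD and 56%. Pairing 5% treated with 6% prevalence (63%) leaves almost no room for refusal, since 6% × 85% = 5.1%. Sensitivity should not be applied again to the 6.5–7.5% yield, which is already detected dementia.
2. State the mixing formula, including the effect given to missed cases and refusers.
3. Restate the observable effect and the unadjusted power with the range, and recompute the table with a row for 0.06 SD.
4. Report power under the planned ANCOVA separately. Say that the effects are in unadjusted SD units, and label the baseline-to-12-month HUI correlation as an assumption with its justification.

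The cost is one rewritten paragraph and one table. Patients, endpoint, analysis and sample size stay as they are. The stated unadjusted power will look less favourable, and a claim of 80% will depend on justifying a correlation.

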Primary Specific Aim 2: Test the impact of dementia screening on the mood and anxiety symptoms of patient at baseline and 1, 6, and 12 months (i.e., primary potential harms).

(We hypothesize that screened subjects will not have higher depression or anxiety at one month post-screening (as measured by the Patient Health Questionnaire (PHQ-9) and Generalized Anxiety Disorder (GAD-7) scales)

Secondary Aims: Estimate the cost effectiveness of dementia screening.

(We hypothesize that screened subjects will have an Incremental Cost Effectiveness Ratio (ICER) below the maximum acceptable threshold of \$100,000 per quality adjusted life year saved at 12 months.)

B. Innovation

Pragmatic

Previous studies by our team and others have demonstrated that routine feedback of dementia screening scores, continuing medical education for dementia, and other passive educational interventions can improve rates of diagnosis, but not patient outcomes.^{12,28-32} We have shown that patients and families perceive potential harms from screening and that dementia screening can result in important incremental health care costs.^{21-23,33} Conversely, we and others have also already demonstrated that collaborative care, focused on non-

pharmacologic approaches to behavioral disturbances, can improve patient outcomes under experimental conditions.^{34,35} The innovation of this trial is in moving the process upstream to asymptomatic, older adults, cared for in typical but prepared community-based practices, to document actual benefits and harms, including costs. “Asymptomatic”, in the case of cognitive impairment, is paradoxical in some respects, but we denote asymptomatic to mean that the cognitive impairment is not a presenting symptom of the patient (just as hypertension is asymptomatic but can be detected by screening, cognitive impairment can be detected through screening tests).

Academic Community Partnership

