[figure not shown]

written materials to assist in caregiver education and support.

Through this summary of our preliminary studies we hope to establish our preparedness for the successful completion of this pragmatic clinical trial of dementia screening in primary care.

E. CHOICE Trial

We are proposing to enroll 4,000 adults, aged 65 and older, attending 10 primary care clinics in Indianapolis; these clinics are representative of two large health care systems: Wishard Health Services (WHS) and IU Health (IUH). We will randomize older adults at ratio of 1:1 into “no screening” or “screening” groups. Subjects randomized into the screening group who have a positive screening would be further referred into a dementia diagnostic assessment and counseling and management program. Our outcomes will be measured at baseline, 1, 6 and 12 months. Using data from our local Regional Health Information Exchange, the Indiana Network for Patient Care (INPC), we will collect health care utilization data of our samples; and monitor new diagnosis, diagnostic testing, and prescribed treatments and referrals. The flow diagram for the proposed study is depicted below.

Subject Recruitment

Established in 1999, the Indiana University Practice Based Research Network (IU-PBRN) consists of 17 primary care centers affiliated with Wishard Health Services and Indiana University Health.⁷³ These two systems serve a diverse population of insured and uninsured patients throughout Indianapolis. More than 110 primary-care physicians practice at these sites. These physicians treat approximately 100,000 patients per year in more than 300,000 visits annually. Using the INPC data repository, IU-PBRN effectively uses informatics tools to streamline patient recruitment and follow-up.⁷³ Since its inception, the IU-PBRN has screened more than 45,000 primary care patients, enrolling more than 17,000 subjects into more than 75 studies. The study team has been utilizing the IU-PBRN since its inception and the successful completion of these projects, described in the Preliminary Studies section, are a testament to

the effectiveness of the IU-PBRN. The IU-PBRN achieved this success through the following informatics innovations.

Centralized Electronic Data Management:

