determine the subject's HRQOL.¹¹¹ The HUI is a generic, utility-based HRQOL instrument applied in patients with a wide range of medical conditions.^{111,112} It has eight attributes: Vision, hearing, speech, ambulation, dexterity, emotion, cognition and pain. The individual health domain scores range from 0.00 (maximum impairment) to 1.00 (no impairment) and the multi-attribute (HUI index) scores, a multiplicative function of individual attribute levels, range from 0.36 to 1.00 with anchors 0.00 = dead and 1.00 = perfect health. Naglie et al found that test-retest reliability exceeded the standard for adequate reliability of 0.70 in those with mild dementia (ICC = 0.75).¹¹³ [name] recently published a paper that provides new evidence regarding the construct validity (including responsiveness) of the HUI in community-based subjects with dementia.¹¹² The mean HUI multi-attribute utility score for 408 primary care patients with dementia was 0.54 (SD = 0.23) and the mean one year change was -0.30 among 240 dementia patients who remained in their own home after one year of receiving dementia care program whereas the mean one year change was -0.76 among 29 dementia patients who moved into a skilled nursing home facility.¹¹²

Mood and Anxiety Outcomes

We will use the **Patient Health Questionnaire–9 (PHQ-9)**¹¹⁴⁻¹¹⁶ and **Generalized Anxiety Disorder Scale (GAD-7)**^{117,118} to determine the impact of screening on our subjects' mood and anxiety at baseline, 1,6, and 12 months. We have used both instruments in various primary care-based research studies including our dementia collaborative care trial.^{34,51,93,114-118} The PHQ-9 is a nine-item depression scale with a total score from 0 to 27 and the GAD-7 is a seven-item anxiety scale with a total score from 0 to 21. Both of these scales are derived from the Patient Health Questionnaire; have good internal consistency and test–retest reliability; as well as convergent, construct, criterion, procedural and factorial validity for the diagnosis of major depression and general anxiety disorder.¹¹⁴⁻¹¹⁸ In our previous primary care studies, the mean

PHQ-9 scores ranged from 3.8 (SD = 5.1) to 4.4 (SD = 5.6) and the mean GAD scores ranged from 2.7 (SD = 3.2) to 3.2 (SD= 3.5).^{34,114-118}

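### The PHQ-9 power claim at one month has almost no reserve, and the plan powers two-sided equivalence although its hypothesis is one-directional (no worse)

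*Combined protocol and SAP*

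**What the plan says.** - **Hypothesis** (Primary Specific Aim 2, called Secondary Aim 1 in the Statistical Plan): "screened subjects will not have higher depression or anxiety at one month post-screening". This points in one direction only.
- **Analysis** (I. Statistical Plan, Secondary Aim 1): ANCOVA of month-1 PHQ-9 and GAD-7 between arms, adjusted for patient characteristics and baseline scores. No margin and no rule for concluding no harm are given.
- **Power** (I. Statistical Plan, last paragraph on power): with all 4,000 subjects counted, the claim is that "we will have greater than 95% power to test the equivalence levels in PHQ-9 and GAD-7 at 1 month". The margins behind it are 0.6 points for PHQ-9, with an SD of 5.1, and 0.5 points for GAD-7, with an SD of 3.2. No significance level, test procedure or month-1 loss is given.
- **SDs from previous studies** (H. Data Collection, Mood and Anxiety Outcomes): "PHQ-9 scores ranged from 3.8 (SD = 5.1) to 4.4 (SD = 5.6"). For GAD-7 the corresponding SDs are 3.2 and 3.5. The power sentence uses the lower SD for each scale.
- **Loss**: the primary-outcome calculation is made "allowing 10% of patients with missing follow-up outcomes at 12 months". No figure is given for month 1.
- **Allocation** (E. CHOICE Trial): "We will randomize older adults at ratio of 1:1 into “no screening” or “screening” groups".

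**The concern.** The plan names depression and anxiety as its primary potential harms, so the month-1 comparison carries the safety side of the benefit-harm question. Two things look weak.

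First, the PHQ-9 figure takes the full 4,000 subjects, the lower SD and, implicitly, 5% per side. If it depends on all of these together, the trial has less assurance than the sentence conveys.

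Second, hypothesis, power statement and analysis describe three different things: no worse, equivalent within a margin, and a comparison of means. A non-significant ANCOVA comparison does not by itself establish absence of harm. A two-sided equivalence criterion can fail because mood improved, which is not harm. With level, margin rule and direction unstated in the analysis, they could be settled after the data are seen.

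**Working it through.** **Inputs.** Margins 0.6 (PHQ-9) and 0.5 (GAD-7). SD 5.1 or 5.6 (PHQ-9), 3.2 or 3.5 (GAD-7). 2,000 per arm with no loss. 1,800 per arm if the 10% allowed at 12 months is assumed to apply at month 1. Level: not stated, so 5% and 2.5% per side are both shown. True difference 0 unless noted. No baseline adjustment unless noted.

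**Formulas** (normal approximation), with SE = SD × √(2/n) and z = 1.645 (5%) or 1.960 (2.5%):
- Two-sided equivalence (two one-sided tests): power = 2Φ(margin/SE − z) − 1
- One-sided non-inferiority: power = Φ(margin/SE − z)

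**The plan's figure.** PHQ-9: SE = 5.1 × √(2/2000) = 0.1613; 0.6/0.1613 = 3.720; 2Φ(3.720 − 1.645) − 1 = 96.2%. GAD-7: SE = 0.1012; 0.5/0.1012 = 4.941; power 99.9%. Both exceed 95%, so the statement reproduces at 5% per side.

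**PHQ-9 under other inputs the documents leave open**

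| n per arm | SD | margin/SE | Equivalence, 5% | Equivalence, 2.5% | Non-inferiority, 5% | Non-inferiority, 2.5% |
|---|---|---|---|---|---|---|
| 2,000 | 5.1 | 3.720 | 96.2% | 92.2% | 98.1% | 96.1% |
| 1,800 | 5.1 | 3.529 | 94.1% | 88.3% | 97.0% | 94.2% |
| 2,000 | 5.6 | 3.388 | 91.9% | 84.7% | 95.9% | 92.3% |
| 1,800 | 5.6 | 3.214 | 88.3% | 79.0% | 94.2% | 89.5% |

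**Break-even for 95% equivalence power at 5% per side.** At SD 5.1, 1,878 evaluable per arm are needed, a loss of (2,000 − 1,878)/2,000 = 6.1%. At SD 5.6, 2,264 per arm are needed, more than are enrolled.

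**GAD-7.** The least favourable case (1,800 per arm, SD 3.5, 2.5% per side) gives 98.0% for equivalence.

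**Baseline adjustment.** ANCOVA replaces SD by SD × √(1 − r²). With 1,800 per arm, PHQ-9 equivalence power returns to 95% at r of about 0.20 (SD 5.1) or 0.45 (SD 5.6) at 5% per side, and at about 0.44 or 0.57 at 2.5%. The documents give no r.

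**Direction.** With true difference d (screened minus not screened), equivalence power = Φ((0.6 − d)/SE − z) + Φ((0.6 + d)/SE − z) − 1. Suppose screening lowers PHQ-9 (1,800 per arm, SD 5.1, SE 0.170, 5% per side):
- d = −0.2: Φ(3.061) + Φ(0.708) − 1 = 76%
- d = −0.3: Φ(3.649) + Φ(0.120) − 1 = 55%

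Non-inferiority power in both cases is above 99%. At d = 0 and 1,800 per arm, the one-sided form gains between about 3 points (97.0 against 94.1, SD 5.1, 5%) and 10.5 points (89.5 against 79.0, SD 5.6, 2.5%).

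**The case against.** The best defence is that the sentence is correct as written: it states its sample size, margins and SDs, and the result follows. That stands. A reader might infer from the table that the claim above 95% is a calculation error; the documents do not support that.

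A reader might also take 88–94% (or 79–88% at 2.5%) as the true power of the no-harm test. That reading fails for three reasons:
- Those are two-sided equivalence figures. For the one-directional hypothesis, power with 10% loss, SD 5.1 and one-sided 5% is 97.0%, still above 95%; at SD 5.6 it is 94.2%, short by less than a point.
- The 10% loss is a 12-month allowance. Using it at month 1 is an assumption, and early loss may be smaller; at 5% loss (1,900 per arm, SD 5.1, 5% per side) equivalence power is 95.2%.
- The figures are unadjusted, whereas the plan specifies ANCOVA, and a moderate baseline correlation would restore 95%. Without a stated correlation, that gain cannot be credited or denied.

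Nor do the documents say which previous study best resembles this population, so SD 5.6 is a possibility, not the expected value. The 76% and 55% figures require a real mood benefit and a formal equivalence test, and the plan commits to neither.

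Two things are left unanswered. The figure drops to 91.9% at SD 5.6 with no loss assumed at all, and nothing in the plan reconciles the hypothesis, the word equivalence and the ANCOVA comparison.

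**Conclusion.** The concern holds as a lack of reserve and a mismatch of test form. The PHQ-9 claim is right only with SD close to 5.1, 5% per side and month-1 loss of at most about 6%, before any credit for baseline adjustment. With the 12-month loss assumed at month 1, equivalence power at 5% per side is 94.1% (SD 5.1) or 88.3% (SD 5.6). Loss alone therefore costs about two points; a material shortfall needs the larger SD or the 2.5% level. GAD-7 power is secure.

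The mismatch matters more. As written, the plan has no pre-stated criterion for its no-harm conclusion, and the equivalence form it powers is stricter than its hypothesis requires. These results rest on the normal approximation, equal arms, and a true difference of zero except where a benefit is stated.

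**What to change.** **In Secondary Aim 1 of the Statistical Plan**, state that no harm is concluded for each scale when the upper confidence limit of the ANCOVA-adjusted month-1 difference (screened minus not screened) lies below the margin already given (0.6 for PHQ-9, 0.5 for GAD-7), at a named one-sided level.

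**In the power paragraph**, restate PHQ-9 power for that test with the assumed month-1 loss and SD 5.1 to 5.6. With 1,800 per arm and no adjustment this is 94–97% at one-sided 5% or 90–94% at one-sided 2.5%. If a baseline correlation is relied on, state it and its source. The claim above 95% can stay for GAD-7. The two-sided equivalence figures should not be printed as the power of the no-harm test.

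The cost is one sentence in each place and, for PHQ-9, a range that may start slightly below 95%. No additional patients, visits or data are required.
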